12.4.4 Sensitivity and Supportive analyses

Sensitivity analyses and supportive analyses will be conducted in order to provide evidence that the results seen from the primary analysis are robust. These analyses will center on the deviations in model assumptions, and the treatment of missing data.

Sensitivity analyses

In order to determine the robustness of the logistic regression model used for the primary analysis, ACR50 response at Week 16, further logistic regression models may be conducted which explore the impact of other BSL or disease characteristics on response.

Supportive analyses

The impact of missing data on the analysis results will be assessed as well by repeating the logistic regression model using ways to handle missing data. These may include, but are not limited to:

- Tipping point analysis

Additional supportive analyses will be conducted to examine the effect of TNF α status (naïve or IR) and/or other cDMARDs along with study drug and/or the effect of treatment discontinuation without rescue medication but remaining in the study on the primary endpoint.

12.5 Analysis of secondary endpoints

12.5.1 Efficacy [REDACTED] endpoint(s)

Efficacy variables

The secondary efficacy variables are listed below. Secondary efficacy variables will be analyzed using the FAS population unless otherwise specified.

- ACR20 response at Week 16
- Minimal disease activity (MDA) response at Week 16

- PASI90 response for psoriasis subset at Week 16
- Change from baseline in PASDAS score at Week 16
- Change from baseline in HAQ-DI[©] score at Week 16
- Change from baseline in SF36-PCS at Week 16
- Change from baseline in FACIT-Fatigue score at Week 16
- Change from baseline in mNAPSI for nail subset at Week 16
- Resolution of dactylitis for dactylitis subset at Week 16
- Resolution of enthesitis for enthesitis subset at Week 16

Testing strategy

- The following hypotheses will be included in the testing strategy, and type-I-errors will be set such that a family-wise type-I-error of 5% is kept:

Primary objectives

[figure not shown]
- H₁: i.v. secukinumab regimen is not different to placebo regimen with respect to ACR50 response at Week 16

Secondary objectives

- H₂: i.v. secukinumab regimen is not different to placebo regimen with respect to ACR20 response at Week 16
- H₃: i.v. secukinumab regimen is not different to placebo regimen with respect to MDA response at Week 16
- H₄: i.v. secukinumab regimen is not different to placebo regimen with respect to PASI90 response at Week 16 in the subset of subjects who have $\geq 3\%$ skin involvement with psoriasis at baseline
- H₅: i.v. secukinumab regimen is not different to placebo regimen with respect to the change from baseline in PASDAS at Week 16
- H₆: i.v. secukinumab regimen is not different to placebo regimen with respect to the change from baseline in HAQ-DI[©] score at Week 16
- H₇: i.v. secukinumab regimen is not different to placebo regimen with respect to change from baseline in SF36-PCS score at Week 16
- H₈: i.v. secukinumab regimen is not different to placebo regimen with respect to change from baseline in FACIT-Fatigue score at Week 16
- H₉: i.v. secukinumab regimen is not different to placebo regimen with respect to change from baseline in mNAPSI score at Week 16 in the subset of subjects with PsA and nail psoriasis at BSL.
- H₁₀: i.v. secukinumab regimen is not different to placebo regimen with respect to resolution of dactylitis response at Week 16 in the subset of subjects who have dactylitis at BSL.
- H₁₁: i.v. secukinumab regimen is not different to placebo regimen with respect to resolution of enthesitis response at Week 16 in the subset of subjects who have enthesitis at BSL.

The graphical approach of (Bretz et al 2009) for sequentially rejective testing procedures is used to illustrate the testing strategy:

Figure 12-1 Hierarchical Testing Strategy

The family-wise error will be set to two-sided $\alpha=5\%$ and it will be controlled with the proposed hierarchical testing strategy.

The hypotheses (H_1) for the primary objective (ACR50 at Week 16) for the i.v. regimen vs. placebo will be tested at α . If H_1 is rejected, then the hypothesis H_2 will be tested at α . If H_2 is rejected, then the hypothesis H_3 will be tested and so on.

Estimand definition for the secondary variables

Estimand definition for the secondary binomial variables is the following:

- A. Population: defined through appropriate inclusion/exclusion criteria to reflect the targeted Psoriatic arthritis population, unless otherwise specified.
- B. Variable: composite of remaining on the study and on randomized treatment through 16 weeks and achieving *variable* response at 16 weeks
- C. Intercurrent event: the intercurrent event is captured through the variable definition
- D. Population-level summary: Difference in marginal response proportions between treatments

The estimand of binary variables is (i.v. secukinumab regimen vs placebo) obtained from a logistic regression model with treatment and randomization stratum (TNF α status –naïve or IR) as factors and weight as a covariate at week 16 in the FAS population. Difference in marginal response proportions will be computed for comparisons of i.v. regimen vs. placebo regimen utilizing the logistic regression model fitted. In the analysis subjects dropping out or being unblinded before week 16 or having missing response data at week 16 are considered as non-responders.

Estimand definition for the secondary continuous variables is the following:

- A. Population: defined through appropriate inclusion/exclusion criteria to reflect the targeted Psoriatic arthritis population
- B. Variable: change from baseline in the *variable* of interest
- C. Intercurrent event: had no intercurrent events occurred before week 16
- D. Population-level summary: difference in variable means between the treatment conditions

The estimand of continuous variables at week 16 is (i.v. regimen vs placebo) obtained from a repeated measures model in the FAS population assuming subjects dropping out or having missing data at week 16 are missing-at-random (MAR). MAR imputation will be implemented through an MMRM model.

ACR20 at Week 16

Response at Week 16 to ACR20 in the FAS will be evaluated using a logistic regression model with treatment and randomization stratum (TNF α status –naïve or IR) as factors and weight as a covariate. Difference in marginal response proportions will be computed for comparisons of i.v. regimen vs. placebo regimen utilizing the logistic regression model fitted.

Minimal disease activity

The proportion of subjects achieving minimal disease activity (MDA) (Coates et al 2010) which is assessed as 5 of the 7 following: ≤ 1 tender joint count, ≤ 1 swollen joint count, PASI ≤ 1 or

BSA \leq 3%, patient pain VAS \leq 15, patient global assessment of disease activity VAS \leq 20, HAQ-DI $^{\circ}$ \leq 0.5, tender enthesal points \leq 1).

Logistic regression model with treatment and randomization stratum (TNF α status –naïve or IR) as factors and weight as a covariate will be used. Difference in marginal response proportions will be computed for comparisons of i.v. regimen vs. placebo regimen utilizing the logistic regression model fitted.

PASI90 response

PASI90 at Week 16 will be evaluated for those subjects in whom the assessment occurred due to sufficient skin involvement (at least 3% BSA affected with psoriasis, which is planned to be a subset of the FAS). These binary variables will be evaluated in the same fashion as ACR response, i.e. a logistic regression model with treatment and randomization strata as factors and weight as a covariate.

Psoriatic Arthritis Disease Activity Score (PASDAS)

Between-treatment differences in the change in PASDAS will be evaluated using a Mixed effect Repeated Measures model (MMRM) with treatment regimen, analysis visit and TNF-alpha inhibitor status as factors, and weight and BSL PASDAS score as continuous covariates. Treatment by analysis visit and BSL by analysis visit will be included as interaction terms in the model. An unstructured covariance structure will be assumed for this model. The significance of the treatment effects for i.v. regimens at different analysis visits will be determined from the pairwise comparisons performed between i.v. regimens and placebo at the appropriate analysis visits.

Physical function (HAQ-DI $^{\circ}$)

Between-treatment differences in the change in HAQ-DI $^{\circ}$ will be evaluated using a MMRM with treatment regimen, analysis visit and TNF-alpha inhibitor status as factors, and weight and BSL HAQ-DI $^{\circ}$ score as continuous covariates. Treatment by analysis visit and BSL by analysis visit will be included as interaction terms in the model. An unstructured covariance structure will be assumed for this model. The significance of the treatment effects for i.v. regimens at different analysis visits will be determined from the pairwise comparisons performed between i.v. regimens and placebo at the appropriate analysis visits.

SF36-PCS

Between-treatment differences in the change from baseline for SF36-PCS summary score will be evaluated using a MMRM with treatment group, analysis visit and TNF-alpha inhibitor status as factors and BSL SF-36 score and weight as continuous covariates. Treatment by analysis visit and BSL SF-36 score by analysis visit will be included as interaction terms in the model. An unstructured covariance structure will be assumed for the model. The significance of the treatment effects for secukinumab regimens at different analysis visits will be determined from the pairwise comparisons performed between secukinumab regimens and placebo at the appropriate analysis visits.

FACIT-Fatigue $^{\circ}$

Between-treatment differences in the change from baseline for FACIT-Fatigue $^{\circ}$ scores will be evaluated using a MMRM with treatment group, analysis visit and TNF-alpha inhibitor status

as factors and BSL and weight as continuous covariates. Treatment by analysis visit and BSL by analysis visit will be included as interaction terms in the model. An unstructured covariance structure will be assumed for the model. The significance of the treatment effects for i.v. regimens at different analysis visits will be determined from the pairwise comparisons performed between i.v. regimens and placebo at the appropriate analysis visits.

Modified Nail Psoriasis Severity Index (mNAPSI)

Between-treatment differences in the mNAPSI change from baseline for scores will be evaluated using a MMRM with treatment group, analysis visit and TNF-alpha inhibitor status as factors and BSL and weight as continuous covariates. Treatment by analysis visit and BSL by analysis visit will be included as interaction terms in the model. An unstructured covariance structure will be assumed for the model. The significance of the treatment effects for i.v. regimens at different analysis visits will be determined from the pairwise comparisons performed between i.v. regimens and placebo at the appropriate analysis visits ([Cassel et al 2007](#)).

Dactylitis at Week 16

Presence of dactylitis at Week 16 in the subset of subjects who have dactylitis at BSL will be evaluated using a logistic regression model with treatment and randomization stratum (TNF α status –naïve or IR) as factors and weight as a covariate.

Enthesitis at Week 16

Presence of enthesitis at Week 16 in the subset of subjects who have enthesitis at BSL will be evaluated using a logistic regression model with treatment and randomization stratum (TNF α status –naïve or IR) as factors and weight as a covariate.

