Subjects who discontinue study treatment or who decide they do not wish to participate in the study further should NOT be considered withdrawn from the study UNLESS they withdraw their consent (see 'Withdrawal of Informed Consent' section). **Where possible, they should return for the assessments indicated** in the Assessment Schedule. If they fail to return for these assessments for unknown reasons, every effort (e.g. telephone, e-mail, letter) should be made to contact the subject/pre-designated contact as specified in the lost to follow-up section. This contact should preferably be done according to the study visit schedule.

If the subject cannot or is unwilling to attend any visit(s), the site staff should maintain regular telephone contact with the subject, or with a person pre-designated by the subject. This telephone contact should preferably be done according to the study visit schedule.

Subjects who prematurely discontinue or withdraw during a specific treatment period (i.e., Week 16 for treatment period 1 or Week 52 for treatment period 2) should return to site 4 weeks after the last study treatment for the final visit within that treatment period. Subjects should also return for the follow-up visit (Week 60) 12 weeks after the last study treatment (see [Table 8-1](#)). The final visit should be performed before any new treatment is initiated.

The investigator must also contact the IRT to register the subject's discontinuation from study treatment.

If discontinuation occurs because treatment code has been broken, please refer to Emergency breaking of treatment code section. Refer to [Section 6.6.3](#).

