12.4.1 Definition of primary endpoint(s)

The primary efficacy variable will be ACR50 response at Week 16. The analysis of the primary efficacy variable will be based on the FAS subjects. Primarily, CRP will be used instead of ESR to calculate ACR response; ESR will only be used in the event CRP is missing.

The primary estimand is defined as follows:

- A. Population: defined through appropriate inclusion/exclusion criteria to reflect the targeted psoriatic arthritis population
- B. Variable: composite of remaining on the study and on randomized treatment through 16 weeks and achieving ACR50 response at 16 weeks
- C. Intercurrent event: the intercurrent event is captured through the variable definition
- D. Population-level summary: Difference in marginal response proportions for comparison between treatments

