12.4.3 Handling of missing values/censoring/discontinuations

Missing data for ACR50 response and other binary efficacy variables (e.g. ACR20, [REDACTED] HAQ-DI[®] response, etc.) for data up to Week 16 will be handled as follows:

- Subjects who drop out of the trial for any reason will be considered non-responders from the time they drop out through Week 16 based on the estimands.
- Subjects who do not have the required data to compute ACR response (i.e. tender and swollen joint counts and at least three of the five ACR core set variables) at BSL and at the specific time point will be classified as non-responders.

Continuous variables (e.g. [REDACTED], [REDACTED], etc.) will be analyzed using a mixed-effects repeated measures model (MMRM) which is valid under the missing at random (MAR) assumption. For analyses of these parameters, if all post-BSL values are missing then these missing values will not be imputed and this subject will be removed from the analysis of the corresponding variable, i.e. it might be that the number of subjects providing data to an analysis is smaller than the number of subjects in the FAS.

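### The MMRM for H5 to H9 keeps values collected after a treatment stop or prohibited rescue, which its hypothetical estimand rules out; the binary scoring lists also omit treatment stops

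*Protocol*

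**What the plan says.** **Continuous endpoints.** Protocol Section 12.5.1 defines the estimand for PASDAS, HAQ-DI, SF36-PCS, FACIT-Fatigue and mNAPSI as the change from baseline "had no intercurrent events occurred before week 16". It names no intercurrent event. The estimate comes from a repeated measures model "assuming subjects dropping out or having missing data at week 16 are missing-at-random (MAR"). Section 12.4.3 and the endpoint paragraphs of 12.5.1 add model terms but no rule on which observed values to exclude.

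**Binary endpoints.** The primary variable in Section 12.4.1 is a "composite of remaining on the study and on randomized treatment through 16 weeks and achieving ACR50 response at 16 weeks". Section 12.5.1 uses the same form for the secondary binary variables. Both sections say that the variable definition captures the intercurrent event. Two scoring sentences follow. In Section 12.4.3, subjects who drop out of the trial are "considered non-responders from the time they drop out through Week 16 based on the estimands", and a second bullet covers insufficient ACR data. In Section 12.5.1, "subjects dropping out or being unblinded before week 16 or having missing response data at week 16 are considered as non-responders".

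**Conduct.** Under Section 9.1.1, a subject who stops study treatment "should NOT be considered withdrawn from the study UNLESS they withdraw their consent", and is asked to return for scheduled assessments where possible. Under Section 6.2.3, rescue with a prohibited biologic before the Week 16 assessments ends study treatment; the section does not say that it ends participation. Section 12.4.4 plans a supportive look at "the effect of treatment discontinuation without rescue medication but remaining in the study on the primary endpoint".

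**SAP.** The supplied SAP covers the final database lock only. Its Introduction says that Week 16 analyses are not repeated, and Section 2.11 says that the Week 16 analysis was already done.

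**The concern.** The plan separates stopping treatment from leaving the study, and expects some subjects to do the first without the second. Those subjects can have Week 16 values measured off drug or on another biologic.

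A hypothetical estimand has no use for such values. An MMRM handles under MAR only what is missing, so values that are present and not excluded enter the likelihood as if the subject were still on the assigned regimen. Run as written, the model mixes the stated hypothetical effect with a treatment-policy effect, in proportions set by how many stoppers return.

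For the binary endpoints the definition and the scoring sentences differ by one component. A programmer who codes from the sentences alone would score an off-treatment responder as a responder, contrary to the definition. What is at stake is whether the reported number answers the stated question. Sample size is not at stake.

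**Working it through.** **1. Which subjects are affected.** Dosing is every 4 weeks and the last dose of treatment period 1 is at Week 12. Sections 8 and 9.1.1 bring a discontinuing subject back 4 weeks after the last dose, and 9.1.1 adds that this is before any new treatment. That visit closes a normal dosing interval. After a Week 12 last dose it falls at Week 16 and is no problem. The affected group is subjects whose last dose was at Baseline, Week 4 or Week 8 and who still attend later scheduled visits, plus subjects who start a prohibited biologic before the Week 16 assessments.

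**2. Definition against rule.**

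| Situation before Week 16, value observed at Week 16 | Stated estimand | Rule as written |
|---|---|---|
| H5 to H9: stopped treatment, stayed in study | value not wanted | value enters the MMRM |
| H5 to H9: prohibited biologic, stayed in study | value not wanted | value enters the MMRM |
| Binary: stopped treatment, stayed in study | non-responder by definition | not named in 12.4.3 or 12.5.1 |
| Binary: emergency unblinding (6.6.3 then requires a drug stop) | non-responder by definition | named in 12.5.1 |

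**3. Size for a continuous endpoint.** Inputs are the 150 mg columns of Table 12-3. For HAQ-DI the difference is 0.44 − 0.21 = 0.23, with SD 0.507 and 190 per arm. Two-sided 5% power for two means is Φ(d / (SD·√(2/190)) − 1.96). The standard error is 0.507 × 0.1026 = 0.0520, so power is Φ(4.42 − 1.96) = 99.3%. The table states 99%.

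The documents give no rate of stopping while staying in the study; Section 5 gives only 10% dropout. Let s be the assumed share of secukinumab subjects observed at Week 16 after a stop and back at the placebo mean. The difference becomes 0.23 × (1 − s):

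| s | HAQ-DI difference | Power |
|---|---|---|
| 0% | 0.230 | 99.3% |
| 2% | 0.225 | 99.1% |
| 5% | 0.219 | 98.7% |
| 10% | 0.207 | 97.8% |

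FACIT-Fatigue (6.18 − 1.98 = 4.20, SD 9.303) behaves the same way: 4.20, 3.99 and 3.78 at 0%, 5% and 10%, with power 99.3%, 98.7% and 97.7%.

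**4. Size for the binary endpoints.** Let p0 and p1 be the Table 12-2 placebo and 150 mg rates, s0 and s1 the stop-but-stay shares, and q0 and q1 the response rates after a stop. The estimand gives p1(1 − s1) − p0(1 − s0). The scoring sentences taken alone add s1·q1 − s0·q0.

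| Stop share, placebo/secukinumab | Response after stop | ACR50: estimand → sentences alone | Enthesitis: estimand → sentences alone |
|---|---|---|---|
| 5%/5% | same in both arms | shift 0 | shift 0 |
| 10%/5% | placebo rate | 26.8 → 26.4 | 20.0 → 18.2 |
| 5%/10% | placebo rate | 24.6 → 25.0 | 15.5 → 17.3 |
| 5%/5% | own arm's rate | 26.4 → 27.8 | 18.2 → 19.2 |

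For example, at 5%/10% the ACR50 estimand is 35.9 × 0.90 − 8.1 × 0.95 = 32.3 − 7.7 = 24.6 points, and the shift is (0.10 − 0.05) × 8.1 = +0.4.

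**5. ACR50 power.** The stated figure of about 99% is reproduced (above 99.9% by the normal approximation). With 10% of secukinumab subjects and no placebo subjects counted as stoppers, the difference is 32.3 − 8.1 = 24.2 points and power is still above 99.9%.

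**The case against.** The strongest reply is that the binary half is already settled. Staying on randomized treatment is part of the variable, the intercurrent event is said to be captured there, and Section 12.4.3 refers back to the estimands. On that view the scoring sentences only add non-responders for missing data. This largely stands. What remains is that two lists meant to be programmed omit one component of the definition, although 12.5.1 goes out of its way to add unblinding.

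For H5 to H9 one can say that a hypothetical estimand with MAR handling shows the intent. It does, but intent is not a rule: no event is named and no observed value is excluded.

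The early final visit narrows the affected group, as shown above. It does not empty it, because Section 9.1.1 also asks stoppers to attend scheduled visits.

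Separate Week 16 rules may exist. The supplied SAP does not contain them, so the point holds only for the documents in hand.

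A reader might infer that the literal rules dilute the treatment effect and cost power on enthesitis and dactylitis. The documents do not support that. The binary shrinkage appears when placebo subjects are assumed to stop more often than secukinumab subjects; it vanishes at equal rates with a common response and reverses when the rates are swapped. Nor do the documents support an inference of inflated type I error, or that the Week 16 results were in fact scored wrongly.

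**Conclusion.** The point holds for H5 to H9. The stated estimand is hypothetical, the plan foresees values after a treatment stop or prohibited rescue, and the MMRM text keeps them. For the six binary endpoints it is a wording alignment, since the definition already gives the answer.

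The likely effect is small. HAQ-DI would move from 0.230 to about 0.219 or 0.207 at 5% or 10% stopping, with power still at 97.8% or more. That rests on assumed stop rates, complete loss of effect after stopping, no rescue effect in either arm, and a two-sample calculation in place of the MMRM. Other behaviour after a stop could change the size or the sign. The binary shift has no fixed direction. The binary figures also assume that the Table 12-2 rates describe subjects still on treatment, which the documents do not say. ACR50 power is not in question.

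**What to change.** In Section 12.5.1, state that H5 to H9 values collected after permanent discontinuation of randomized treatment, or after the start of a prohibited biologic, are set to missing in the MMRM. Exempt the final visit 4 weeks after the last dose if it is made before any new treatment. Add a supportive analysis that uses all observed values.

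In the non-responder lists of Sections 12.4.3 and 12.5.1, add permanent discontinuation of randomized treatment.

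Because the Week 16 analysis preceded the supplied SAP and its own rules were not supplied, the study report should give the number of such subjects per arm, how they were scored, and the aligned analysis if it differs from the one that was run.

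The cost is a few sentences, one count table and at most one rerun of existing models, with no new visits or data. A change to the protocol text needs a formal amendment under Section 14.1. The statistical price is reliance on MAR after stops for lack of efficacy, which can be optimistic; the supportive analysis with all observed values shows how much depends on it.
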